#### **11.1.4. Clinical Laboratory Abnormalities and Other Abnormal Assessments**

Abnormal clinical laboratory findings (e.g., clinical chemistry) will be reported as an AE unless the value was outside normal laboratory limits at baseline and did not increase by a severity grade level at the follow-up assessment. Grade 2 or greater results for any other laboratory test will be considered clinically significant.

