
4-hour period after the start of dosing. Sitting (3 minutes) vital signs will be taken during screening, at clinic check in, pre-dose, then at 15, 30, 60 minutes and 2, 4, 6, 12, 24, and 48 hours post dose. A 12-lead ECG will be obtained prior to dosing, then at 2, 6, 12, 24, and 48 hours post dose. When vital signs or ECG are scheduled at the same time as a PK blood draw, these assessments will be performed before drawing any blood. The FOBT will be performed at screening, clinic intake on Day -1, pre-discharge on Day 3, and at follow-up on Day 7. Subjects will return for a final follow-up visit 7±2 days after discharge for a final safety assessment including vital signs, ECG, AEs, FOBT, Stool Consistency Questionnaire, GI Symptoms Checklist, and clinical laboratory tests.
Number of Subjects (Planned): 32
Main Inclusion/Exclusion Criteria: Healthy male or female volunteers, aged 18-to-55 years, with body mass index (BMI) between 18 and 32 kg/m  (inclusive)
Investigational Product, Dosage, and Mode of Administration: Kindolor tosylate will be supplied as enteric coated tablets containing 100 mg and 300 mg drug product for oral administration. Tablets will be consumed orally with 240 mL of water under observation by a study staff member.
Reference Therapy, Dosage, and Mode of Administration: Placebo enteric-coated tablets identically matched to investigational product tablets will be consumed orally. Enteric coated tablets, with an equal amount of Prosolv SMCC replacing the drug product, will be provided as the placebo.
Duration of Study: Each subject will participate in the study for up to 58 days for females and 120 days for males, including up to 30 days for screening, 4 days and 3 nights residing in the Phase I unit, with one follow-up visit 7 ± 2 days after discharge, with a telephone call check at 28 days after dosing for females and 90 days after dosing for males for a verification contraceptive practices, and conformance with agreement not to donate ova, breastfeed, or donate sperm during this period.
Criteria for Evaluation: Safety: AEs, physical examinations, clinical laboratory data, ECG, FOBT, Stool Consistency Questionnaire, GI Symptoms Checklist, urine output over 24 hours, and vital signs. Pharmacokinetics: AUC ∞ , AUC t , C max , t max , λ z , t 1/2

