#### **11.1.1. Adverse Event Definition**

An AE is any untoward medical occurrence in a clinical investigation subject administered a pharmaceutical product and may not necessarily have a causal relationship with the administered treatment. An AE can therefore be any unfavorable and unintended sign (including a clinically significant laboratory abnormality), symptom, or disease temporally associated with the use of an investigational product, whether or not related to the investigational product. Pre-existing conditions, diseases, or disorders are not considered AEs unless there is a change in severity or frequency.

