#### 11.1.6. Reporting Pregnancy

Pregnancy in a study subject within 30 days after study drug administration must be reported to the investigator within 1 working day of becoming aware of the pregnancy. Subjects who become pregnant during the screening period prior to study drug administration will not be randomized to receive treatment.

If the subject becomes pregnant during the study or up 30 days after study drug administration, then a Pregnancy Reporting Form must be completed and emailed to Fast-Track within 24 hours of becoming aware of the pregnancy. Pregnancies must be followed to conclusions and an updated Pregnancy Reporting Form should be emailed to Fast-Track within 24 hours of becoming aware of the conclusion of the pregnancy.

Pregnancy in a study subject is not considered an AE. However, the medical outcome of an spontaneous abortion, stillbirth, or congenital anomaly is considered an SAE and must be reported to the sponsor within 24 hours of the site becoming aware of the event.

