#### 11.1.7. Classification of Adverse Event Intensity and Relationship to Investigational Product

The severity of AEs or SAEs will be in accordance with the FDA's "Toxicity Grading Scale for Healthy Adult and Adolescent Volunteers Enrolled in Preventive Vaccine Clinical Trials". For those not listed in the guidance, the following criteria will be used:

Mild:	An event that is usually transient, requiring no special treatment, and does not generally interfere with the subject's daily activities.
Moderate:	An event that interferes with usual activities of daily living, causing discomfort but poses no significant or permanent risk of harm to the subject. The event is usually ameliorated with additional specific therapeutic intervention.
Severe:	An event that interrupts usual activities of daily living or significantly affects clinical status. The event poses a significant risk of harm to the subject and hospitalization may be required, and typically requires intensive therapeutic intervention.

However, as gastric AEs are a potential concern, and the toxicity grading scale stated above, does not cover some of the more serious gastric AEs such as gastritis and gastric ulcer, the Common Toxicity Criteria for Adverse Events Grading Scale (version 5.0) will be used for the severity of these AEs.

The investigator must assess relationship to the investigational product based on the following criteria:

Unrelated:	The subject did not receive the investigational product, the temporal sequence of the AE/SAE onset relative to administration of the investigational product is not reasonable, or there is another obvious cause of the AE/SAE.
Unlikely:	There is evidence of exposure to the investigational product but there is another more likely cause of the AE/SAE.
Possible:	There is evidence of exposure to the investigational product, the temporal sequence of the AE/SAE onset relative to administration of the investigational product is reasonable, but the AE/SAE could have been due to another equally likely cause.
Probable:	There is evidence of exposure to the investigational product, the temporal sequence of the AE/SAE onset relative to administration of the investigational product is reasonable, and the AE/SAE is more likely explained by the investigational product than by any other cause.

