**Table 7: Clinical Laboratory Tests**

Hematology	Clinical Chemistry	Coagulation	Urinalysis	Other
Hematocrit Hemoglobin RBC count WBC count Absolute counts for: Neutrophils Lymphocytes Monocytes Basophils Eosinophils Platelets	Albumin ALT AST BUN Creatinine Direct Bilirubin Total Bilirubin Alkaline phosphatase CPK LDH Sodium Potassium Chloride Calcium Bicarbonate Inorganic Phosphorus Uric Acid Total Cholesterol Total Protein Glucose Triglycerides	PT aPTT Fibrinogen INR	Specific gravity pH Ketones Protein Blood Glucose Nitrites Leukocyte esterase A microscopic evaluation will be performed if blood or leukocyte esterase are detected.	Amylase Lipase

Serum creatinine levels will be used to calculate creatinine clearance (CrCl) according to the Cockcroft-Gault (1976) formula as follows:

$$\text{Males} \quad \text{CrCl (mL/min)} = \frac{(140 - \text{age in years}) \times \text{body weight in kg}}{72 \times \text{serum creatinine mg/dL}}$$

$$\text{Females} \quad \text{CrCl (mL/min)} = \frac{0.85 \times (140 - \text{age in years}) \times \text{body weight in kg}}{72 \times \text{serum creatinine mg/dL}}$$

In circumstances where creatinine clearance is overestimated when using actual weight in overweight patients, use ideal weight as the adjustment per standard practice. If estimated creatinine clearance is not overestimated using actual weight, use actual weight in the Cockcroft formula instead of the ideal body weight. This will avoid underestimations that may occur when using ideal body weight in the normal weight population while also reducing overestimations that may result when using actual weight in overweight individuals.

Ideal body weight may be used to adjust for subjects with a BMI of over 25 kg/m^2 as needed:

Estimate Ideal body weight in (kg)

Males: IBW = 50 kg + 2.3 kg for each inch over 5 feet.

Females: IBW = 45.5 kg + 2.3 kg for each inch over 5 feet.

For any laboratory test value outside the reference range that the investigator considers clinically significant:

- The investigator will repeat the test to verify the out-of-range value
- The investigator will follow the out-of-range value to a satisfactory clinical resolution
- A laboratory test value will be reported as an AE with the severity score assigned in accordance with the FDA Guidance for "Toxicity Grading Scale for Healthy Adult and Adolescent Volunteers Enrolled in Preventive Vaccine Clinical Trials"

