5.2 Safety Endpoints

Adverse Events (AEs): An AE is defined as any reaction, side effect, or untoward event that occurs during the course of the clinical trial, whether or not the event is considered related to the investigational agent or clinically significant. For this study, AEs will include events reported by the subject, observed by clinical staff, clinically significant abnormal clinical laboratory results, or a positive pregnancy test. Reports of AEs will be elicited by a verbal probe (e.g., “How are you feeling?”) administered starting on Day 1 and daily during residency and at all other clinic visits.

Any events spontaneously reported by the subject or observed by the investigative staff will also be recorded. Each AE will be graded for severity, and the date and time of onset, cessation and resolution will be recorded.

Severity: All AEs (except application site reactions described below) will be graded according to the following definitions. Assignment of grade based on the intensity of symptoms and the degree of limitation of usual daily activities will be done according to severity using the following criteria:

- Grade 1:** Mild symptoms invoking a minimum degree of discomfort that are easily tolerated.
- Grade 2:** Moderate symptoms that result in a reduction in normal daily activity, but is not totally incapacitating. This may or may not require medical intervention.
- Grade 3:** Severe symptoms that may be totally incapacitating or result in marked reduction in normal daily activity. Medical intervention is usually required.
- Grade 4:** Potentially life-threatening event that requires emergency intervention or hospitalization.

Relationship: The degree of certainty for which the AE/SAE is attributed to the investigational product or alternative causes (e.g. natural history of the underlying disease, concomitant therapies, etc.) should be determined by how well the experience can be understood in terms of one or more of the following. The relatedness of an AE to the study drug is the best estimate of the causal relationship between the study drug and an AE at the time of reporting. Causality will be assessed by the Principal Investigator or designee.

The following drug relationships will be used for this clinical study:

Unrelated: There is no temporal relationship between the event and the administration of the study drug or the event is clearly due to the subject’s medical condition, other therapies, or accident.

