Unlikely: There is evidence of exposure to the study drug but there is another more likely cause of the event.

Possibly Related: There is some temporal relationship between the event and the administration of the study drug and the event is unlikely to be explained by the subject's medical condition or other therapies.

Probably Related: The temporal relationship between the event and the administration of the study drug is compelling, and the subject's medical condition and other therapies cannot explain the event.

Definitely Related: The event follows a reasonable temporal sequence from administration of the medication or follows a known or suspected response pattern to the medication.

The categories of Definitely, Probably, and Possibly will be considered investigational product related with regards to summary statistics.

Serious Adverse Events. Each AE or reaction will be classified by the study investigator as serious or non-serious. The International Conference on Harmonization (ICH) Guideline for Industry: Clinical Safety Data Management: Definitions and Standards for Expedited Reporting, ICH-E2A March 1995, as implemented by the U.S. Food and Drug Administration defines SAE or reaction as any untoward medical occurrence that at any dose:

- results in death;
- is life-threatening; (*NOTE: The term "life-threatening" in the definition of "serious" refers to an event in which the subject was at risk of death at the time of the event; it does not refer to an event which hypothetically might have caused death if it were more severe.*)
- requires inpatient hospitalization or prolongation of existing hospitalization;
- results in persistent or significant disability/incapacity; or
- is a congenital anomaly/birth defect.

In addition, important medical events that may not result in death, be life-threatening, or require hospitalization may be considered a serious adverse drug reaction, when based on appropriate medical judgment that may jeopardize the subject and may require medical or surgical intervention to prevent one of the outcomes listed in the above definition.

Physical Examination.: A physical examination of the oral cavity, head, eyes, ears, nose, and throat, cardiovascular system, lungs, abdomen, extremities, skin, neuropsychiatric mental status and sensory/motor status, musculoskeletal system and general appearance will be performed during screening, weeks 4, 8, and 12.

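### AE rates are not uniquely defined, because protocol and SAP give conflicting rules for laboratory AEs, pregnancy, severity, causality and the collection window

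*Protocol*

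**What the plan says.** **Laboratory values.** Protocol 11.1.4 reads: "Abnormal clinical laboratory findings (e.g., clinical chemistry) will be reported as an AE unless the value was outside normal laboratory limits at baseline". The exemption also requires that the severity grade did not rise at follow-up. No clinical-significance condition is attached, although the next sentence treats Grade 2 or higher on any other test as clinically significant. Protocol 11.3 places AE reporting among the steps that follow "For any laboratory test value outside the reference range that the investigator considers clinically significant". SAP 5.2 lists among AEs "clinically significant abnormal clinical laboratory results, or a positive pregnancy test". The general AE definition in protocol 11.1.1 mentions laboratory findings only in a parenthesis: "including a clinically significant laboratory abnormality".

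**Pregnancy.** Protocol 11.1.6: "Pregnancy in a study subject is not considered an AE". SAP 5.2, as just quoted, includes a positive test.

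**Severity.** Protocol 11.1.7 uses the FDA toxicity scale for healthy volunteers, a mild/moderate/severe fallback for events not listed there, and CTCAE version 5.0 for the more serious gastric events. SAP 5.2 grades all AEs from 1 to 4 by intensity of symptoms and limitation of activity, and gives no laboratory thresholds.

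**Causality.** In protocol 11.1.7, Possible requires exposure and reasonable timing, "but the AE/SAE could have been due to another equally likely cause". In SAP 5.2, Possibly Related reads: "There is some temporal relationship between the event and the administration of the study drug and the event is unlikely to be explained". The alternatives it has in mind are illness in the subject or other treatment. The SAP counts Possibly, Probably and Definitely as related. Both texts have five categories; the key to SAP Listings 16-18 has four.

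**Timing.** The protocol synopsis sets the final visit "7±2 days after discharge for a final safety assessment", and sections 5 and 8.12 also count from discharge. Section 8.8 counts the same interval from the dosing day, and Table 5 gives Study Day 7±2. Section 11.1.3 has AEs assessed until the final visit and also reported up to one week after dosing. Section 11.1.8 puts the end of the reporting period 7 days after the final visit.

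**The concern.** Safety and MTD are the primary objective, and AEs are one of the listed safety endpoints. The cohort tables for the DSMB and the final AE tables both need one answer to four questions: is this an AE, how severe, related or not, and inside the window or not. Here two people following different sections could give different answers for the same subject. With six active subjects per dose, a few reclassified subjects visibly change a percentage.

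The laboratory rule has the largest potential effect on the overall AE rate. A rule that makes each new out-of-range result an AE brings chance reference-range excursions into the AE tables of every arm, placebo included.

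**Working it through.** **1. The plan's own AE figure.** Protocol 12.4 and SAP 7 give the chance of at least one AE in six subjects. With 1 − (1 − p)^6:

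- p = 10%: 1 − 0.90^6 = 46.9% (stated 47%)
- p = 15%: 1 − 0.85^6 = 62.3% (stated 62%)
- p = 20%: 1 − 0.80^6 = 73.8% (stated 74%)
- p = 25%: 1 − 0.75^6 = 82.2% (stated 82%)

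All four reproduce. The arithmetic is sound; the open point is what counts as an AE.

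**2. Where the laboratory rules part.** A new, mild excursion that the investigator does not consider significant is an AE under 11.1.4, but is not put forward as one by 11.3 or SAP 5.2. For tests covered by the Grade 2 sentence in 11.1.4, results of Grade 2 or above are clinically significant anyway, so the rules agree there. The gap is mainly Grade 1 or ungraded values. For the tests with their own cut-offs in 11.1.5 (hematocrit, hemoglobin, BUN, creatinine, ALT, AST), the exact gap depends on grade tables that the documents do not reproduce.

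**3. Illustrative size.** The protocol's laboratory table (Table 7) lists 21 chemistry, 10 hematology and 4 coagulation tests plus amylase and lipase: 21 + 10 + 4 + 2 = 37 blood tests. Table 5 schedules two post-dose panels (Day 3 and follow-up), so 37 × 2 = 74 values per subject. The documents give no excursion rate, so q, the chance of a new excursion per value, is assumed. The share of subjects with at least one is 1 − (1 − q)^k.

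| q | 10 effective tests per panel, k = 20 | 37 tests per panel, k = 74 |
|---|---|---|
| 1% | 1 − 0.99^20 = 18% | 1 − 0.99^74 = 52% |
| 2% | 1 − 0.98^20 = 33% | 1 − 0.98^74 = 78% |
| 5% | 1 − 0.95^20 = 64% | 1 − 0.95^74 = 98% |

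The right-hand column treats all 74 values as independent and is an upper end. The middle column allows for correlation by assuming 10 effective tests per panel.

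**4. Final visit and AE window, with dosing on Day 1 and discharge on Day 3.**

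- After discharge: 3 + 5 to 3 + 9 = Days 8-12.
- After dosing: 1 + 5 to 1 + 9 = Days 6-10.
- Table 5: 7 − 2 to 7 + 2 = Days 5-9.

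Only Days 8-9 satisfy all three. The window then closes at the final visit (anywhere from Day 5 to Day 12), one week after dosing (1 + 7 = Day 8), or 7 days after the final visit (5 + 7 = Day 12 to 12 + 7 = Day 19).

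**5. Which output each conflict reaches.**

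- Laboratory rule, pregnancy and window: whether an event enters the AE tables at all.
- Severity: the severity tables, and potentially the AE parts of stopping criteria ii (moderate AEs in one SOC) and iii (a severe AE) in protocol 8.13.2. A symptom-free laboratory abnormality can carry a toxicity grade under 11.1.7 and 11.3, but has no natural place on the SAP's symptom scale.
- Causality: the related-AE results only (for example SAP Tables 7-11). An event with an equally likely alternative cause is Possible, hence related, under the protocol, but does not meet the SAP's Possibly Related. No criterion in 8.13.2 uses causality.
- Laboratory parts of criteria i and iii: these use laboratory grade directly, so it does not matter whether the value is also called an AE.

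**The case against.** Several parts of the opposing case stand.

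- The wording in 11.1.1 is inclusive and does not contradict 11.1.4. SAP 5.2 also says what AEs will include, and its opening sentence covers events whether or not clinically significant. Section 11.3 never says that other values are not AEs. Restriction to significant values is thus an inference, though the natural one: 11.3 and SAP 5.2 would have no reason to name clinical significance if every new excursion already counted.
- Protocol 12.3.2 fixes the counting rule: once per subject per preferred term, at the highest severity.
- The excursion rate and the number of effective tests are assumptions. The percentages describe any excursion among many tests, so they are not like for like with the 10-25% scenarios in the sample-size text. AEs will also be tabulated by SOC and preferred term beside pooled placebo.
- The investigator grades events under the protocol, and the SAP says that it expands on the protocol's analysis. One could therefore expect the protocol scale to prevail. But SAP 5.2 states its own grading and causality definitions without deferring. Its mentions of application site reactions and of assessments at weeks 4, 8 and 12 do not fit a single oral dose, which suggests carried-over text.
- Reporting up to one week need not mean that collection stops then, and 11.1.8 mainly concerns follow-up of unresolved events. Even so, 11.1.8 uses the term reporting period, and no section says which limit governs the tables.

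A reader might infer that primary AE rates are undefined, that noise would certainly dominate them, or that the laboratory-AE rule unsettles the stopping criteria and MTD. The documents support none of these: no AE-rate endpoint is named as primary, no excursion rate is given, and the laboratory stopping criteria run on grade.

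**Conclusion.** The point holds as an inconsistency: AE rates are not uniquely defined. The five conflicts differ in weight. The laboratory rule could matter most for the overall AE rate: 18% to 64% of subjects with a chance laboratory AE under 11.1.4 for q of 1% to 5% and 10 effective tests per panel, and up to 52% to 98% if all 37 tests are independent. These figures rest wholly on the assumed q and independence, and the same background would be expected on placebo. The severity conflict is the one that can reach the AE parts of stopping criteria ii and iii. Causality moves the related-AE tables only, and pregnancy is minor. The final-visit definitions overlap on two days, and the possible end of AE collection runs from Day 5 to Day 19. It should be corrected, since the fix is almost entirely wording.

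**What to change.** 1. Reconcile protocol 11.1.4 with 11.3 and SAP 5.2 to one laboratory-AE rule, using the protocol's own clinical-significance criteria: Grade 2 or higher (11.1.4), the cut-offs in 11.1.5, and investigator judgement under 11.3. Keeping that judgement matters, because a lower-grade change that the investigator considers significant should still be an AE.
2. Report other excursions in the SAP summary and shift tables. Urinalysis has a summary table (Table 20) but no shift table and no listing, so add a urinalysis listing.
3. In SAP 5.2, delete the positive pregnancy test from the AE definition, replace the severity and relationship text with protocol 11.1.7, and give Listings 16-18 the same five relationship categories.
4. Reconcile the final-visit timing (protocol sections 1, 5, 8.8, 8.12 and Table 5) and the AE window (11.1.3 and 11.1.8) to one definition. Which timing to use is for the sponsor and the investigator to decide.

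Cost: protocol and SAP wording and one added listing, with no change to sample size. Downside: fewer minor laboratory events in the AE tables, which the laboratory tables and listings must then show.
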